5. STUDY DESIGN

This is an open-label study comparing the safety of two treatment cohorts in which radioembolization will be administered using the device SIR-Spheres in combination with regorafenib to patients with mCRC with liver metastases. The two treatment cohorts will be evaluated for safety, ORR, PFS, and OS. Twenty-five patients will be treated in each cohort. The first cohort will complete enrollment before the second cohort opens. There will be no randomization or blinding.

A safety review for toxicity by the Medical Monitor will occur after the first 10 patients have been enrolled in each cohort and treated with one cycle of regorafenib and SIR-spheres (combination therapy) to assess the frequency of \geq Grade 3 adverse events and all SAEs. Accrual will not be halted while the analysis is being conducted.

Stopping Rules Due to Toxicities of Combination Therapy

Stopping rules due to toxicities assessed as related to combination therapy by the Medical Monitor will be defined as follows:

CONFIDENTIAL

STUDY DEVICE: SIR-Spheres®

SCRI INNOVATIONS STUDY NUMBER: GI 189

DATE OF ORIGINAL PROTOCOL: 16 December 2013

Date of Amendment #1: 15 April 2014

Version 2.0

- A patient death considered to be caused by AEs of combination therapy
- A patient with Grade 4 AST, ALT, or irreversible hepatic failure assessed as related to combination therapy;
- More than 2 patients that develop Grade 3 AST, ALT, or total bilirubin assessed as related to combination therapy;
- More than 2 patients develop Grade 3 bleeding in the lung, stomach, small intestine, or liver assessed as related to combination therapy.

If the early stopping rules are met or safety signals emerge from the group of the first 10 patients treated with combination therapy in each cohort, patient recruitment will discontinue and the study will be reassessed. Any outcome of these safety reviews will be communicated in a timely manner to the participating investigators so that they may notify their IRBs.

Blood samples will be collected from all patients prior to the hepatic angiogram and ^{99m}Tc MAA lung shunt scan, on Day 8 after SIR-Spheres treatment, and Day 30 (pre-dose) after SIR-Spheres treatment (see Section 5.1). Expressions of cytokines and proteins will be measured to explore potential biomarkers that may correlate with clinical outcome. The study schema is presented in Figure 1.

CONFIDENTIAL

STUDY DEVICE: SIR-Spheres®

SCRI INNOVATIONS STUDY NUMBER: GI 189

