- Biomarker blood sample collection prior to the hepatic angiogram and 99m Tc MAA lung shunt scan
- CEA tumor marker

The following tests will be obtained 7-4 days prior to SIR-Spheres treatment:

- Hepatic angiogram
- 99m Tc MAA lung shunt scan

7.3.5 Cycle 2, Day 1

SIR-Spheres may not be administered until the patient's hematologic, liver and renal function assessments performed per Section 7.3.4 have been re-confirmed as eligible according to Section 3.1 by the Investigator.

- SIR-Spheres treatment
- BP

CONFIDENTIAL

STUDY DEVICE: SIR-Spheres®

SCRI INNOVATIONS STUDY NUMBER: GI 189

DATE OF ORIGINAL PROTOCOL: 16 December 2013

Date of Amendment #1: 15 April 2014

Version 2.0

7.3.6 Cycle 2, Day 8

- BP
- AE assessment
- CMP
- Biomarker blood sample collection (following SIR-Spheres treatment)

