7.4.4 Cycle 2, Day 1 (± 72 hours)

Regorafenib may not start until the patient's hematologic, liver and renal functions have been re-confirmed as eligible according to Section 3.1 by the Investigator. Therefore, the regorafenib cycle starts on the day that treatment begins. If liver function toxicities are present, patient may be rechecked weekly for 2 additional weeks. Those patients with persistent liver function toxicities after this time will come off study, but will be followed until resolution.

CONFIDENTIAL

STUDY DEVICE: SIR-Spheres®

SCRI INNOVATIONS STUDY NUMBER: GI 189

DATE OF ORIGINAL PROTOCOL: 16 December 2013

Date of Amendment #1: 15 April 2014

Version 2.0

- Physical examination, weight, and vital signs
- BP
- ECOG PS
- AE assessment
- Concomitant medication review
- CBC
- CMP
- PT/PTT/INR (for patients receiving Coumadin therapy)
- CEA tumor marker
- Biomarker blood sample collection (Day 30 following SIR-Spheres treatment only)

7.4.5 Cycle 2, Day 8 and 15

- Physical examination, weight, and vital signs
- BP
- ECOG PS
- AE assessment
- Concomitant medication review
- CBC
- CMP
- PT/PTT/INR (for patients receiving Coumadin therapy)

7.4.6 Cycle 2, Day 22

- BP

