10.4.3 Early Safety Monitoring and Stopping Rules

A safety review for toxicity by the Medical Monitor will occur after the first 10 patients have been enrolled in each cohort and treated with one cycle of regorafenib and SIR-spheres (combination therapy) to assess the frequency of \geq Grade 3 adverse events and all SAEs. Accrual will not be halted while the analysis is being conducted.

Stopping Rules Due to Toxicities of Combination Therapy

Stopping rules due to toxicities assessed as related to combination therapy by the Medical Monitor will be defined as follows:

- A patient death considered to be caused by AEs of combination therapy

CONFIDENTIAL

STUDY DEVICE: SIR-Spheres®

DATE OF ORIGINAL PROTOCOL: 16 December 2013

Date of Amendment #1: 15 April 2014

SCRI INNOVATIONS STUDY NUMBER: GI 189

Version 2.0

- A patient with Grade 4 AST, ALT, or irreversible hepatic failure assessed as related to combination therapy;
- More than 2 patients that develop Grade 3 AST, ALT, or total bilirubin assessed as related to combination therapy;
- More than 2 patients develop Grade 3 bleeding in the lung, stomach, small intestine, or liver assessed as related to combination therapy.

If the early stopping rules are met or safety signals emerge from the group of the first 10 patients treated with combination therapy in each cohort, patient recruitment will discontinue and the study will be reassessed. Any outcome of these safety reviews will be communicated in a timely manner to the participating investigators so that they may notify their IRBs.

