11.1.5 Recording and Reporting of Adverse Events

Recording of Adverse Events

All AEs of any patient during the course of the research study will be recorded in the eCRF, and the investigator will give his or her opinion as to the relationship of the AE to the study material or process (i.e., whether the event is related or unrelated to study drug administration, SIR-Spheres microspheres or SIRT procedure).

All AEs should be documented. A description of the event, including its date of onset and resolution, whether it constitutes a serious adverse event (SAE) or not, any action taken (e.g., changes to study treatment), and outcome, should be provided, along with the investigator’s assessment of causality (i.e., the relationship to the study treatment[s]). For an AE to be a suspected treatment-related event there should be at least a reasonable possibility of a causal relationship between the protocol treatment and the AE. Adverse events will be graded according to the NCI CTCAE v4.0, and changes will be documented.

If the AE is serious, it should be reported immediately to SCRI Innovations Safety Department. Other untoward events occurring in the framework of a clinical study are to be recorded as AEs (i.e., AEs that occur prior to assignment of study treatment that are related to a protocol-mandated intervention, including invasive procedures such as biopsies, medication washout, or no treatment run-in).

Any clinically significant signs and symptoms; abnormal test findings; changes in physical examination; hypersensitivity; and other measurements that occur will be reported as an AE, and collected on the relevant eCRF screen.

CONFIDENTIAL

STUDY DEVICE: SIR-Spheres®

SCRI INNOVATIONS STUDY NUMBER: GI 189

DATE OF ORIGINAL PROTOCOL: 16 December 2013

Date of Amendment #1: 15 April 2014

Version 2.0

Test findings will be reported as an AE if: the test result requires an adjustment in the study drug(s) or discontinuation of treatment, and/ or test findings require additional testing or surgical intervention, a test result or finding is associated with accompanying symptoms, or a test result is considered to be an AE by the investigator.

CONFIDENTIAL

STUDY DEVICE: SIR-Spheres®

SCRI INNOVATIONS STUDY NUMBER: GI 189

DATE OF ORIGINAL PROTOCOL: 16 December 2013

Date of Amendment #1: 15 April 2014

Version 2.0

Reporting Period for Adverse Events

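### The early safety review and recruitment stop rest on patients who received both modalities, so patients whose toxicity ends treatment after the first are not clearly covered, and the events left out differ by cohort

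*Protocol*

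**What the plan says.** Protocol Sections 5 and 10.4.3 carry the same text. The Medical Monitor reviews Grade 3 or higher adverse events and all SAEs once the first 10 patients have been "enrolled in each cohort and treated with one cycle of regorafenib and SIR-spheres (combination therapy"). The list of rules is introduced by "Stopping rules due to toxicities assessed as related to combination therapy by the Medical Monitor will be defined as follows". One related death, or one related Grade 4 transaminase elevation or irreversible hepatic failure, is enough. The Grade 3 liver rule reads "More than 2 patients that develop Grade 3 AST, ALT, or total bilirubin assessed as related to combination therapy", and a similar rule covers Grade 3 bleeding. The action follows if the rules are met or if safety signals "emerge from the group of the first 10 patients treated with combination therapy in each cohort, patient recruitment will discontinue". Accrual continues during the review.

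The second modality is conditional on organ function in both cohorts. In Cohort 1 (Section 7.3.5), SIR-Spheres waits until the hematologic, "liver and renal function assessments performed per Section 7.3.4 have been re-confirmed as eligible according to Section 3.1". In Cohort 2 (Section 7.4.4), regorafenib waits for the same confirmation, with up to two further weekly rechecks of liver toxicity, after which: "Those patients with persistent liver function toxicities after this time will come off study, but will be followed until resolution". Section 7.3.7 applies the same consequence in Cohort 1 when regorafenib is due to restart after SIR-Spheres.

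The final analysis is broader. Section 10.3 puts everyone with at least one dose of study treatment in the Safety Population, and Section 11.2 requires every SAE to be reported within 24 hours whatever its cause. The SAP (Section 1.4) ticks a safety review and no independent monitoring committee, and defines no separate population for that review.

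**The concern.** Entry to the reviewed group depends on tolerating the first modality well enough to be given the second, so the group is filtered on the outcome being monitored. A patient whose first modality causes lasting liver, blood or renal toxicity may never qualify.

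The filter also acts at a different point in each sequence. The primary objective is the safety of the two sequences, and this is the only interim safety review that the SAP plans. If the review is read as limited to patients with both modalities, early toxicity looks milder than it was, and each cohort is screened for a different set of events. A recruitment stop that should follow from early, treatment-ending toxicity could then come late or not at all.

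**Working it through.** The documents state no operating characteristics for the stopping rules, so there is no planned figure to reproduce. The check compares the texts first and then illustrates the size.

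**Who falls inside the group of patients with both modalities**

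| Toxicity that ends study treatment | Cohort 1 | Cohort 2 |
|---|---|---|
| During the first regorafenib cycle | Before SIR-Spheres: outside (Section 7.3.5) | After SIR-Spheres: can be inside, if a partial cycle qualifies |
| After SIR-Spheres, before the next regorafenib dose | Both modalities received: inside (Section 7.3.7) | One modality received: outside (Section 7.4.4) |
| After regorafenib is resumed or under way | Inside | Inside, with the same proviso on a partial cycle |

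The first two rows show the imbalance, and it runs in both directions. The protocol does not say whether an incomplete regorafenib cycle satisfies the one-cycle condition.

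**How often someone is left out**

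Let q be the share of starters who stop for toxicity before the second modality, assumed independent between patients. The documents do not give q; 5%, 10% and 20% are assumptions. The number X of such patients before the 10th combination-treated patient is negative binomial:

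P(X = k) = C(9 + k, k) × q^k × (1 − q)^10

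- q = 0.05: P(0) = 0.95^10 = 0.599; P(1) = 10 × 0.05 × 0.599 = 0.299; P(2) = 55 × 0.0025 × 0.599 = 0.082. At least one: 40%. Three or more: 2%.
- q = 0.10: P(0) = 0.349; P(1) = 10 × 0.10 × 0.349 = 0.349; P(2) = 55 × 0.01 × 0.349 = 0.192. At least one: 65%. Three or more: 11%.
- q = 0.20: P(0) = 0.107; P(1) = 10 × 0.20 × 0.107 = 0.215; P(2) = 55 × 0.04 × 0.107 = 0.236. At least one: 89%. Three or more: 44%.

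Three is the relevant number for the Grade 3 rules, which need more than two patients.

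**What a strict reading would do to the Grade 3 liver rule**

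Let p be the true rate of related Grade 3 liver toxicity and f the share of affected patients who never receive the second modality. Both are assumptions. Among counted patients the rate becomes p(1 − f)/(1 − pf), and the chance of meeting the rule is P(at least 3 of 10).

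- p = 0.20: 32.2% if all starters count; with f = 0.5 the counted rate is 0.10/0.90 = 0.111 and the chance is 9.1%.
- p = 0.30: 61.7% if all starters count; with f = 0.5 the counted rate is 0.15/0.85 = 0.176 and the chance is 25.3%.
- f = 1: 0% at any p.

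A concrete case: 14 Cohort 2 patients receive SIR-Spheres, 4 have related Grade 3 bilirubin that blocks regorafenib, and 10 continue without an event. The strict count is 0 of 10. Among all who started it is 4 of 14.

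**The case against.** The strongest reply is that the text fixes when the review happens, not whom it covers. It is timed by 10 combination-treated patients, but no sentence confines the tabulation of adverse events to them. The four rules are limited by attribution, not by a patient list, and the reference to the first 10 may attach only to emerging signals. A Medical Monitor could therefore read it broadly. This stands, and it is why the point is that coverage is unclear. But nothing requires the broad reading, and one person's discretion is not a pre-specified rule.

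Four stronger inferences are tempting, and the documents do not support them.

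- *These patients count nowhere.* They remain in SAE reporting (Section 11.2), in the reporting of deaths not due solely to progression (Section 11.3.4), and in the final safety summaries (Sections 10.3 and 10.4.4). These routes do not themselves trigger the recruitment stop. The termination provision in Section 11.4.3 covers only unanticipated device effects.
- *Cohort 2 alone is under-monitored.* The regorafenib lead-in in Cohort 1 is the mirror case, and the net direction is unknown. Section 8.1.3 places radioembolization-induced liver disease typically at 4-8 weeks, while regorafenib starts at 2-4 weeks in Cohort 2, so much of it can count in both cohorts. Patients who recover after a delay proceed and count.
- *The 40%, 65% and 89% are chances of missing a stopping event.* They are chances of any excluded toxicity stop. Even three or more excluded patients would matter to the Grade 3 liver rule only if each had a related Grade 3 liver event.
- *The rules cannot be applied because adverse events carry no combination category.* Section 11.1.5 asks "whether the event is related or unrelated to study drug administration, SIR-Spheres microspheres or SIRT procedure", but does not make these options exclusive, and Section 10.4.3 gives the combination judgement to the Medical Monitor. The two should be reconciled; they do not contradict each other.

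It is also fair to say that aiming the stop at combined toxicity may be deliberate, since both products are commercially available. Counting first-modality toxicity under unchanged thresholds is a real trade-off, which the sponsor should decide.

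**Conclusion.** The concern holds for the interim review and the stopping rules, and not for the final safety analysis. As worded, the plan does not clearly cover patients stopped by toxicity after the first modality, and the uncovered events differ between the two sequences being evaluated. With assumed stop rates of 5% to 20%, at least one such patient per cohort is likely or nearly so (40% to 89%), and three or more range from uncommon to fairly common (2% to 44%). These figures rest on the assumed q and on independence between patients. The lost sensitivity of the Grade 3 liver rule applies only under the strict reading and depends on assumed p and f. This is a low-cost improvement to the early review, worth making because the study's primary objective is safety.

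**What to change.** In Protocol Sections 5 and 10.4.3:

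- Keep the review timing at the 10th combination-treated patient in each cohort, so that the amount of combination experience at review does not shrink.
- State that the review covers every patient in the cohort who has started any study treatment by then, in line with the Safety Population in Section 10.3.
- Include patients who stopped for toxicity before the second modality and show them separately. List apart those removed only because the angiogram or lung-shunt scan made them ineligible (Section 5.1).
- State whether toxicity that prevents the second modality counts toward the stopping rules, and whether a partial regorafenib cycle satisfies the one-cycle condition.
- Reconcile relatedness to combination therapy with the relatedness options in Section 11.1.5.

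No threshold is proposed. The cost is protocol wording in two places and slightly more tabulation; the data are already collected. The downside is that toxicity from the first modality alone may enter the review, which the separate display makes visible.

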10.4.4 Safety Analysis

Safety will be assessed through the analysis of the reported incidence of treatment-emergent AEs. Treatment-emergent AEs are those with an onset on or after the initiation of therapy, and will be graded according to NCI CTCAE v 4.03. A copy of CTCAE scoring system may be downloaded from: http://evs.nci.nih.gov/ftp1/CTCAE/CTCAE_4.03_2010-06-14_QuickReference_8.5x11.pdf. AEs that occur prior to initiation of therapy (after consent is signed, i.e. during mapping for SIR-Spheres treatment), will also be assessed.

The AEs will be coded using Medical Dictionary for Regulatory Activities (MedDRA), and summarized using system organ class and preferred term by cohort for all patients in the Safety Population. In addition, summaries of SAEs, AEs leading to treatment discontinuation, AEs by maximum NCI CTCAE grade, and AEs related to study treatment will also be presented by treatment cohort.

Other safety endpoints including laboratory results will be summarized for all patients in the Safety Population.

Concomitant medications will be coded using the World Health Organization-Drug Dictionary and they will be listed and summarized by treatment cohort.

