1.2 Rationale for the Study

Radioembolization using SIR-Spheres microspheres (SIR-Spheres) to treat liver-only or liver-dominant mCRC has been successful in this refractory setting. The combination of regorafenib and SIR-Spheres is an attractive option as an anti-tumor and maintenance treatment for the refractory CRC population.

The proper sequencing of this combination of regorafenib and SIR-Spheres is currently unclear. We propose this two arm study (25 patients in each arm) to evaluate the safety of the combination of regorafenib and SIR-Spheres, with one cohort of patients receiving regorafenib for three weeks followed by a one week hold of regorafenib (regorafenib half-life is 28 hours, one week to allow for washout), followed by SIR-Spheres treatment, followed by re-initiation of regorafenib two to four weeks later, and the other cohort of patients receiving SIR-Spheres followed by the initiation of regorafenib two to four weeks later.

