2. STUDY OBJECTIVES

2.1 Primary Objectives

The primary objective of this study is:

- To evaluate the safety of two treatment cohorts combining regorafenib and SIR-Spheres in patients with refractory mCRC with liver metastasis.

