10.3 Analysis Population

The following analysis populations will be used:

- Intent-To-Treat Population (ITT) is defined as all patients who have started study treatment (Radioembolization with SIR-Spheres ^{90}Y or regorafenib).
- Safety Population is defined as all patients who have received at least one dose of study treatment. In this instance, the ITT and safety populations would consist of the same patients.

CONFIDENTIAL

STUDY DEVICE: SIR-Spheres®

SCRI INNOVATIONS STUDY NUMBER: GI 189

DATE OF ORIGINAL PROTOCOL: 16 December 2013

Date of Amendment #1: 15 April 2014

Version 2.0

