 Early Progression Rate (EPR)			
 Time To Progression (TTP)	Default: Estimates of medians in each treatment arm		
 Progression-Free Survival (PFS)	 Other quartiles or percentages of survival required, specify: probability evaluated at 6 month intervals		
 Overall Survival (OS)	 Hazard ratio & 95% confidence interval between treatment arms, unstratified		
 Duration of Response	 p-value, specify statistical test:		
 Duration of Stable Disease	 Hazard ratio & 95% confidence interval between treatment arms, stratified (specify stratification factor(s)):		
 Time To Treatment Failure (TTF)	 p-value, specify statistical test:		
 Other, Specify:			
7 Safety			
Adverse Events	Definition of Treatment-Emergent Adverse Event (TEAE): any adverse event (AE) that starts or worsens after the start of the first dose of study treatment up to 30 days post last dose.		
Laboratory Data	Data will be summarized by:  NCI-CTCAE for CTCAE-gradable parameters, and H/L for non-CTCAE-Gradable parameter		

H/L for all lab parameters

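### The planned adverse-event tables describe each sequence from first dose but do not isolate the combined phase that the primary objective concerns

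*Protocol*

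**What the plan says.** The primary objective (Protocol Section 2.1) is "To evaluate the safety of two treatment cohorts combining regorafenib and SIR-Spheres in patients with refractory mCRC with liver metastasis".

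Section 10.4.4 sets the start of counting: "Treatment-emergent AEs are those with an onset on or after the initiation of therapy". AEs are then "summarized using system organ class and preferred term by cohort for all patients in the Safety Population". SAP section 7 counts any event that "starts or worsens after the start of the first dose of study treatment up to 30 days post last dose". SAP Table 8, the only AE table the SAP lists, shows treatment-related AEs by grade on the safety set.

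On who is counted, Section 10.3 says: "Safety Population is defined as all patients who have received at least one dose of study treatment". It adds that this is the same group as the ITT population, "all patients who have started study treatment (Radioembolization with SIR-Spheres", with regorafenib named as the alternative. One dose of either component is therefore enough.

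On Cohort 1, Section 1.2 describes "one cohort of patients receiving regorafenib for three weeks followed by a one week hold of regorafenib" before SIR-Spheres. Section 7.3.5 adds a gate: "SIR-Spheres may not be administered until the patient's hematologic, liver and renal function assessments performed per Section 7.3.4 have been re-confirmed as eligible". Section 7.2 places the angiogram and lung shunt scan in week 4 for Cohort 1 and at Screening for Cohort 2. Under Section 5.1 a patient found unsuitable by either test is removed and replaced.

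On Cohort 2, Section 7.4.4 takes patients off study if liver toxicity persists beyond the extra rechecks, so some may never start regorafenib.

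The early review and stopping rules (Section 10.4.3) concern patients who have had both regorafenib and SIR-Spheres.

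**The concern.** The objective is about combining two treatments, but no planned AE table is confined to patients or time in which both had been given. A Cohort 1 row mixes three things: regorafenib-alone events before SIR-Spheres, events after it, and a denominator that includes people who never received it. Restricting to treatment-related events, as SAP Table 8 does, does not separate them, because lead-in regorafenib events are treatment-related too.

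The liver shows what is at stake. Section 6.2.1 says that regorafenib has been associated with severe drug-induced liver injury. Section 8.1.3 describes radioembolization-induced liver disease appearing typically 4 to 8 weeks after treatment. A single whole-period hepatic rate in Cohort 1 cannot tell the reader how often liver injury followed SIR-Spheres in patients pre-treated with regorafenib. In a study with no hypothesis test, the tables are the result.

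**Working it through.** The plan gives no figure on this point. Its one precision statement (Section 10.2) concerns the response rate and is not in question. The sizes below therefore rest on stated assumptions.

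**1. Who stays in the denominator**

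| Route out before both components | Cohort 1 | Cohort 2 |
|---|---|---|
| Mapping failure (5.1, 7.2) | Week 4, after regorafenib: in Safety Population | Screening, before any treatment: not in it |
| Laboratory criteria not re-met or liver toxicity persisting (7.3.5, 7.4.4) | In, without SIR-Spheres | In, without regorafenib |
| Progression, toxicity, withdrawal (3.3) | In | In |

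Section 5.1 replaces mapping failures, but nothing in Section 10.3 removes them from the population.

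**2. Dilution of events that can occur only after SIR-Spheres (Cohort 1)**

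Let k of 25 never receive SIR-Spheres and m = 25 − k. A true rate p is shown as p × m/25. With zero events among m patients, the exact two-sided 95% upper limit is 1 − 0.025^(1/m). The chance of seeing at least one event of true rate 5% is 1 − 0.95^m.

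For a range of k, I read the medians for regorafenib in Protocol Section 1 as exponential, with 28 days = 0.92 months:
- OS 6.4 months: 1 − 2^(−0.92/6.4) = 9.5%, about 2 of 25.
- PFS 1.9 months: 1 − 2^(−0.92/1.9) = 28.5%, about 7 of 25.

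This is illustrative only. No CT is scheduled between baseline and SIR-Spheres, so the upper end would rarely be documented, while mapping and laboratory failures would add to either end.

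| k (assumed) | m | 20% shown as | 30% shown as | Upper limit, 0 events in m | Chance of ≥1 event at 5% |
|---|---|---|---|---|---|
| 0 | 25 | 20.0% | 30.0% | 13.7% | 72% |
| 2 | 23 | 18.4% | 27.6% | 14.8% | 69% |
| 5 | 20 | 16.0% | 24.0% | 16.8% | 64% |
| 7 | 18 | 14.4% | 21.6% | 18.5% | 60% |

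At k = 5, 4/20 = 20% becomes 4/25 = 16%. If instead k patients are replaced so that 25 reach SIR-Spheres, the factor is 25/(25 + k): 25/28 = 0.89 for k = 3 and 25/30 = 0.83 for k = 5.

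**3. Mixing within Cohort 1**

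Let q be the risk of an event in the lead-in, p the risk after SIR-Spheres, and a the share never reaching it, all independent. The ever-event rate is q + (1 − q) × p × (1 − a).
- q = 30%, p = 20%: 0.30 + 0.70 × 0.20 = 44% with a = 0; 0.30 + 0.70 × 0.20 × 0.80 = 41% with a = 20%.
- q = 10%, p = 20%: 28% and 24%.

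The rate after SIR-Spheres is 20% throughout. The pooled row does not recover it.

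**4. Scheduled regorafenib from first dose**

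With a 2-week rest and no delay:
- Cohort 1: Days 1–21, SIR-Spheres Day 29, then Days 43–63, next course from Day 71.
- Cohort 2: SIR-Spheres Day 1, then Days 15–35 and 43–63, next course from Day 71.

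Cumulative dosing days are 21 and 7 at Day 21, 21 and 21 at Day 35, and 42 and 42 just before Day 71. The totals are equal from Day 35 on. If both cohorts wait d extra days after SIR-Spheres, they are equal from Day 35 + d.

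**The case against.** **The whole-period table is legitimate.** Cohort 1 is defined as one cycle of regorafenib, then SIR-Spheres, then regorafenib (Section 10.1), and Section 10.2 speaks of evaluating the two sequences. Toxicity that prevents SIR-Spheres is a consequence of that order. This stands: the table should remain and is not invalid.

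**Much of the information is already planned.** Disposition by cohort (Section 10.4.1), SIR-Spheres exposure and discontinuation reasons (SAP tables) and causality by drug, device and procedure (Section 11.1.5) are all there. This stands in part. It shows that the data exist, but none of it gives AE rates by phase or in patients who had both components. The SAP's statement that patients are analysed by treatment actually received could support a regorafenib-only group, but none is defined or tabulated.

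**The dilution is small and assumed.** Exact 95% intervals are about 6% to 44% for 4/20 and 5% to 36% for 4/25. This stands as to size. It does not make the denominator right.

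**Phase tables have their own bias.** Cohort 1 patients who reach SIR-Spheres have tolerated regorafenib and re-met laboratory criteria, whereas Cohort 2 patients start SIR-Spheres unselected in that sense. This stands and must be stated alongside the added tables.

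**A stronger reading is tempting.** A reader might infer that the lead-in gives Cohort 1 an extra regorafenib course and so inflates its totals against Cohort 2. At the scan six weeks after SIR-Spheres, Cohort 1 has had 42 dosing days and Cohort 2 has had 21. At an assumed 20% risk per course, that is 1 − 0.8² = 36% against 20%. The documents do not support this. The two scans fall on Day 71 and Day 43, while the AE window runs from first dose to 30 days after the last. On that clock the exposures coincide from Day 35. A patient who stops at the earlier Cohort 2 scan would have less exposure, but that comes from scan timing, not from pooling the lead-in.

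**Conclusion.** The concern holds as a gap in the planned output. Nothing planned isolates AEs in patients who have received both components, and the denominators treat the cohorts differently for mapping failures. The membership facts follow directly from the definitions. The size does not: the loss before SIR-Spheres is unknown, and 2 to 7 of 25 is an illustrative range under which a 20% rate is shown as 18.4% to 14.4%.

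A reader should not infer that the planned tables are biased in a known direction between cohorts. Lead-in events raise the Cohort 1 ever-event rate above its rate after SIR-Spheres, patients never combined lower it for events that only SIR-Spheres can start, and Cohort 2 has its own SIR-Spheres-only phase and its own patients never combined. The net effect depends on the event type. I class this as a cheap improvement.

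**What to change.** In Section 10.4.4, SAP section 7 and the SAP table list:

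1. Keep the whole-period AE table by cohort as the summary of each sequence.
2. Add AE tables by onset period within cohort: before SIR-Spheres; from SIR-Spheres to the first later regorafenib dose; from that dose on. The denominator is the patients who entered each period.
3. Base statements on combination safety on patients who received both components, counting from the date of the second one: SIR-Spheres in Cohort 1, first regorafenib in Cohort 2. Taking everyone after SIR-Spheres would not do, since in Cohort 2 that still includes patients who never start regorafenib.
4. Report by cohort the number who never received both components, with reasons and with mapping failures shown separately. State in Section 10.3 how replaced mapping failures are counted.

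The cost is SAP wording, table shells and programming. AE onset dates are already recorded, and exposure to both components is already tabulated. Two drawbacks should be written into the plan: period denominators are smaller, and Cohort 1 patients who reach SIR-Spheres are selected for tolerating regorafenib. The period tables therefore supplement the whole-period comparison and do not replace it.
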